P1	Proximal Popliteal Artery

LIST OF ACRONYMS

P2	Mid Popliteal Artery
P3	Distal Popliteal Artery
PA	Peroneal Artery
PAD	Peripheral Arterial Disease
PCI	Percutaneous Coronary Intervention
PI	Principal Investigator
PIC	Patient Implant Card
POD	Perioperative Death
PLT	Platelets/platelet count
PT	Posterior Tibial Artery
PSVR	Peak Systolic Velocity Ratio
PT / INR	Prothrombin time / International Normalized Ratio
PTA	Percutaneous Transluminal Angioplasty
RMA	Returned Materials Authorization
RS	Residual Stenosis
RVD	Reference Vessel Diameter
SADE	Serious Adverse Device Effect
SAE	Serious Adverse Event
SFA	Superficial Femoral Artery
SVS	Society of Vascular Surgery
TBI	Toe Brachial Index
TMA	Transmetatarsal Amputation
TPT	Tibioperoneal Trunk
TASC	Trans-Atlantic Inter-Society Consensus
TcPO 2	Transcutaneous Oximetry
TIA	Transient Ischemic Attack
TP	Toe Pressure
TL	Target Lesion
TLR	Target Lesion Revascularization
TV	Target Vessel
TVR	Target Vessel Revascularization
UADE	Unanticipated Adverse Device Effect
WIFI	W ound, I schemia, f oot I nfection Score
WIQ	Walking Impairment Questionnaire
% DS	Percentage Diameter Stenosis

## 2. STUDY SYNOPSIS

Study Title:	Tack Optimized Balloon Angioplasty Study for the Below The Knee Arteries Using the Tack Endovascular System® (TOBA II - BTK)
Study Design:	This is a prospective, multi-center, single-arm, non-blinded study designed to investigate the safety and efficacy of the Tack Endovascular System.
Study Objective:	To evaluate the safety and efficacy of the Tack Endovascular System in subjects with below the knee (BTK) peripheral artery disease (PAD) as compared to a pre-defined performance goal (PG) established from published, peer reviewed scientific literature related to below-the-knee (BTK) PAD.
Study Device:	4F Tack Endovascular System manufactured by Intact Vascular, Inc.
Intended Use:	The Tack Endovascular System is intended for use in the Mid/Distal Popliteal, Tibial, and Peroneal Arteries ranging in diameter from 1.5mm to 4.5mm for the treatment of post percutaneous transluminal balloon angioplasty (PTA) dissection(s) requiring repair.
Subject Population:	Subjects with BTK PAD who receive PTA in the Mid/Distal Popliteal, Tibial, and Peroneal Arteries and have a resulting dissection(s) that the Investigator would otherwise treat by means such as, but not limited to, additional angioplasty with extended inflation time or stenting, are eligible for enrollment. To be enrolled, subjects must meet all inclusion criteria and not meet any of the exclusion criteria.
Device Regulatory Status:	4F Tack Endovascular System is a Class III Investigational Device within the United States and Class IIb within the European Union and has been designed and is manufactured by Intact Vascular, Inc. under the control of Intact Vascular’s Quality Management System. Intact Vascular is ISO 13485 certified.
Enrollment:	Up to 232 subjects will be enrolled at up to 60 U.S. and International clinical sites. Each clinical site can enroll a maximum of 46 patients, establishing an enrollment cap at 20% of the subject sample size. The follow-up period for enrolled subjects that receive at least one Tack® implant is 36 months.
Primary Endpoints:	
Safety: Freedom from major adverse limb events (MALE) plus perioperative death (POD) at 30 days defined as a composite of all-cause death, above-ankle target limb amputation, or major re-intervention to the target lesion(s) (defined as new bypass graft, jump/interposition graft revision, or thrombectomy / thrombolysis)
 
Efficacy: Freedom from MALE at 6 months + POD at 30 days

Secondary Efficacy Endpoints:	
 
▪ Target lesion(s) tacked segment(s) patency at 6 months defined as the presence of blood flow using duplex ultrasound. If angiography is available within the 6-month follow-up visit window, it should be used in place of the duplex ultrasound. Evidence of no blood flow within the Tacked segment indicates restenosis/loss of patency.
 
▪ Target Limb Salvage defined as freedom from any above-ankle target limb amputation at 6 months.
 

**Observational Endpoints:**

- Device Success: Successful deployment of the Tack implant(s) at the intended target site(s) and successful withdrawal of the delivery catheter from the introducer sheath.
- Target Lesion Success: Demonstrated target lesion patency [ $<30\%$  residual diameter stenosis (DS), by visual estimate] without the use of a bailout stent within the target lesion upon completion of the index procedure. This will be assessed for all lesions treated with a Tack implant. In addition, target lesion success will also be analyzed by lack of bailout stent to tacked segment only. Multiple target lesions treated as one lesion with PTA will be analyzed as one lesion.
- Procedural Success: Demonstrated target lesion patency ( $<30\%$  residual DS, by visual estimate) without the use of a bailout stent within the target lesion and without the occurrence of MALE+POD upon completion of the index procedure
- Amputation-free survival (AFS): Freedom from above-ankle target limb amputation or all-cause death at 6 and 12 months
- Freedom from MALE at 12 months + POD at 30 days
- Target lesion(s) tacked segment(s) patency at 12 months defined as the presence of blood flow using duplex ultrasound.
- Target Limb Salvage defined as freedom from any above-ankle target limb amputation at 12 months
- Assisted primary target lesion Tacked segment patency (flow vs. no flow) at 6 and 12 months
- Secondary target lesion Tacked segment patency (flow vs. no flow) at 6 and 12 months
- PSVR patency at 6 and 12 months [Freedom from binary restenosis defined as Peak Systolic Velocity Ratio (PSVR) of  $\geq 2.5$  and/or angiographic percent diameter stenosis of  $\geq 50\%$ ] assessed for the following:
  - Target Lesion(s), defined as the entire contiguous arterial segment treated with angioplasty, inclusive of an additional proximal and distal margin of 5 mm
  - Tacked Segment(s), defined as the Tack device and 5 mm of artery proximal and distal to each Tack. If Tacks are within 10 mm of each other, they will be considered as a single tacked segment for the purposes of this patency assessment.
- Clinically-driven target lesion revascularization (CD-TLR) through 6 and 12 months
- Clinically-driven target vessel revascularization (CD-TVR) through 6 and 12 months
- All-cause death through 6 and 12 months
- Any Target vessel revascularization (TVR) through 6 and 12 months

	
 
▪ Any Target lesion revascularization (TLR) through 6 and 12 months
 
 
In addition, the following observational endpoints will be assessed at various time points through 36 months (See Time and Events Schedule Section 8.1):
 
 
▪ Changes in Wound, Ischemia, and foot Infection (Wifi) Classification
 
▪ Changes in ankle brachial index (ABI) and toe brachial index (TBI)
 
▪ Changes in Rutherford Classification
 
▪ Changes in the EQ-5D-3L quality of life questionnaire
 
▪ Changes in the Walking Impairment Questionnaire (WIQ)
 
▪ Tack implant Integrity via X-ray (only performed at 12-month visit)
 
▪ Progress of wound(s) present at study entry (healed, improved, unchanged, worsening, amputated)
 
▪ Appearance of new wound(s) after study entry
 
▪ Unplanned below-ankle target limb amputation(s): digit or transmetatarsal
 

Inclusion Criteria:
	
 
1. Males or non-pregnant females <math>\geq 18</math> years of age at the time of consent
 
2. Female subjects of childbearing potential must have a negative pregnancy test prior to treatment and must use some form of contraception (abstinence is acceptable) through the duration of the study
 
3. Subject has been informed of and understands the nature of the study and provides signed informed consent to participate in the study. If the subject possesses the ability to understand and provide informed consent but due to physical inability, the subject cannot sign the informed consent form (ICF), an impartial witness may sign on behalf of the subject
 
4. Willing to comply with all required follow-up visits
 
5. Rutherford Classification 4 or 5
 
6. Wifi Wound grade of 0, 1 or modified 2
 
7. Wifi Foot Infection grade of 0 or 1
 
8. Estimated life expectancy <math>\geq 1</math> year
 


Angiographic Inclusion Criteria:
	
 
1. Reference vessel diameter is between 1.5 mm and 4.5 mm, inclusive (by visual estimate)
 
2. Only one limb requires treatment during the Index Procedure
 
 
Note: If the subject has bilateral BTK disease, the Investigator should choose the limb that most closely meets eligibility criteria. If the chosen limb does not meet final eligibility after PTA treatment, the subject should not be enrolled at that time. This subject may be brought back for potential study device treatment to the contralateral limb per the

 Joseph L. Mills, Sr, MD, [name], David G. Armstrong, DPM, MD, PhD, [name], [name], [name], MPH, and [name], on behalf of the Society for Vascular Surgery Lower Extremity Guidelines Committee, The Society for Vascular Surgery Lower Extremity Threatened Limb Classification System: Risk stratification based on Wound, Ischemia, and foot Infection (Wifi). J Vasc Surg. 2014; Volume 59, Issue 1, Pages 220-234.e2

protocol requirements. Only one limb may receive study device treatment.

3. Ability to cross study device(s) antegrade through target lesion
4. Has de novo or restenotic target lesion(s) with pre-PTA stenosis of  $\geq 70\%$  or is occluded (by visual estimate) and is indicated for PTA treatment with a standard balloon catheter

**Note:** Diseased segments with  $>30$  mm of healthy vessel between them are considered separate target lesions

**Note:** If any part of the lesion is restenotic, no part of the lesion should have more than 1 prior failure (by plain balloon angioplasty only), which must have occurred greater than 1 year (360 days) prior to the index procedure

**Note:** After PTA treatment, the target lesion is defined as the entire contiguous arterial segment length treated with angioplasty

5. Target lesion(s) located in the mid popliteal (P2), distal popliteal (P3), tibioperoneal trunk, peroneal, anterior tibial, or posterior tibial arteries

**Note:** The mid popliteal artery (P2) begins at the superior aspect of the patella. The most distal location of the tibial and/or peroneal artery(ies) ends at the beginning of the dorsalis pedis artery (DP). Tacks may not be implanted within 1 cm above radiographic tibiotalar joint.

6. Target vessel(s) reconstitute(s) at or above the ankle or displays normal terminal branching

- If the target vessel is the peroneal artery, the artery must display normal terminal branching.
- If the target vessel is the anterior tibial (AT) artery or the posterior tibial (PT) artery, the artery(ies) must display reconstitution at least 1cm proximal to the radiographic tibiotalar joint line, and continue into an intact runoff vessel (AT/ dorsalis pedis or PT/plantar artery).
- If the target vessel is the P2 and/or P3, any 1 of the 3 distal arteries must show respective outflow.
- If the target vessel is the TPT, then respective outflow for either the peroneal artery or posterior tibial artery must be confirmed.

**Note:** Normal terminal branching and/or reconstitution of run-off vessels as described above should be confirmed prior to PTA treatment of the target lesion(s) as well as after PTA treatment to the target lesion(s) (prior to Tack deployment)

	
7. Patent (<50% DS by visual estimate) arterial inflow from aortic bifurcation to the distal edge of the proximal popliteal artery (P1) at the superior end of the patella.
 
Note: Treatment of inflow artery lesions within the iliac (ipsilateral or contralateral), common femoral, superficial femoral, and/or the proximal popliteal (P1) artery(ies) is allowed during the index procedure but must have documented success (<30% residual DS and no major vascular complications) prior to target lesion treatment.
 
Note: If an inflow lesion requires treatment with atherectomy or requires surgical intervention, the patient should not be enrolled
 
8. After PTA treatment, the target lesion has <30% residual DS and presence of at least one post-PTA dissection (by visual estimate) that the Investigator would otherwise treat by means such as but not limited to additional angioplasty, with longer inflation time or stenting
 
9. No evidence of aneurysm or acute thrombus in target vessel


Exclusion Criteria:
	
1. Is pregnant or refuses to use contraception through the duration of the study
 
2. Previous bypass graft in the target limb
 
3. Acute limb ischemia, defined as symptom onset occurring less than 14 days prior to the index procedure
 
4. Prior or planned above-ankle amputation or complete transmetatarsal amputation to the target limb (this does not apply to ray amputation of <math>\leq 2</math> digits, simple digital amputations or ulcer debridements)
 
5. Wifi Foot Infection grade 2 or 3
 
6. Any systemic infection or immunocompromised state. Patients with an ascending infection/deep foot infection or abscess/white blood count (WBC)<math>\geq 12,000</math>/or febrile state
 
7. Endovascular or surgical procedure (not including diagnostic procedures, planned simple digital amputation or wound debridement) to the target limb less than 30 days prior to or planned for less than 30 days after the index procedure
 
8. Existing stent implant in the target vessel
 
9. Any other endovascular or surgical procedure (not including diagnostic procedures, planned simple digital amputation or wound debridement) less than 14 days prior to the index procedure or planned procedure less than 30 days after the index procedure
 
10. Known coagulopathy, hypercoagulable state, bleeding diathesis, other blood disorder, or a platelet count less than 80,000/microliter or greater than 500,000/microliter
 
11. Wifi Wound grade of 2 or 3.

	
 
12. Any subject in which antiplatelet, anticoagulant, or thrombolytic therapy is contraindicated
 
13. Myocardial infarction, coronary thrombolysis or angina less than 30 days prior to the Index Procedure
 
14. History of stroke or transient ischemic attack (TIA) less than 90 days prior to the Index Procedure
 
15. Currently on dialysis
 
16. Known hypersensitivity or contraindication to nickel-titanium alloy (Nitinol)
 
17. Participating in another ongoing investigational clinical trial in which the subject has not completed the primary endpoint(s)
 
18. Has other comorbidities that, in the opinion of the investigator, would preclude them from receiving this treatment and/or participating in study-required follow-up assessments
 
19. Known hypersensitivity or allergy to contrast agents that cannot be medically managed
 
20. Subject already enrolled into this study
 
21. Restenotic target lesion previously treated by means other than plain balloon angioplasty and/or less than 1 year prior to index procedure.
 


Angiographic Exclusion Criteria:
	
 
1. Acute vessel occlusion or acute or sub-acute thrombosis in target lesion
 
2. Subject has significant stenosis (<math>\geq 50\%</math> DS) or occlusion of inflow arteries (including the iliac, superficial femoral and proximal popliteal arteries) not successfully treated (<math>< 30\%</math> residual DS and without major complication) prior to PTA of target lesion
 
3. The target lesion shows no dissections after PTA or dissections of a lesser grade for which the operator would normally not pursue additional treatment
 
4. If parallel non-target vessel (anterior tibial, peroneal, or posterior tibial) is treated during index procedure and is not successful (<math>< 30\%</math> residual DS and without major complication) prior to PTA of target lesion/vessel
 
5. Below the ankle lesion requiring treatment
 
6. Use of atherectomy, cryoplasty, cutting/scoring/contoured balloon angioplasty, stenting or any other treatment (with the exception of a crossing device) of the target lesion/vessel other than plain balloon angioplasty PTA during the index procedure
 
 
Note: Use of atherectomy in a parallel, non-target vessel is allowed during the index procedure but must have documented success (<math>< 30\%</math> residual DS and no major vascular complications) prior to target lesion/vessel treatment

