#### 4.2. REPORT OF PRIOR INVESTIGATIONS

Intact Vascular has developed the Tack Endovascular System, a system designed to provide apposition of dissected tissue with an implantable, cylindrical nitinol (nickel-titanium) Tack implant following percutaneous transluminal balloon angioplasty (PTA). Intact Vascular is currently conducting a clinical study in below-the-knee arteries (TOBA-BTK) and a United States pivotal investigation device exemption (IDE) study of the 6Fr device in the femoropopliteal arteries.

The TOBA-BTK Study (Prospective, Multicenter Tack Optimized Balloon Angioplasty Below the Knee (TOBA - BTK) Study for Infrapopliteal Arteries Using the *Tack Endovascular System*® (Protocol# TD 0109 Rev D)) is a prospective, single arm, multi-center, first in man study designed to collect data in support of safety and performance of the Intact Vascular *Tack Endovascular System*® for tissue apposition in peripheral arteries with reference vessel diameters (RVD) ranging from 1.5-4.5mm. Specifically, the population for this study included subjects with critical limb ischemia (Rutherford Class 4-5) that had angiographic evidence of type A-F dissection following below the knee (BTK) percutaneous transluminal angioplasty (PTA). TOBA-BTK was a feasibility study designed to assess 30-day safety and ease of use. Long-term follow-up will be conducted through 24 months. Currently, data through 12 months is available.

The inclusion criteria for the TOBA-BTK study was:

- Rutherford 4 or 5
- RVD 1.5 – 4.5mm
- Lesion located between knee joint and ankle
- De novo lesion  $\geq 70\%$  stenotic or occluded
- Up to 2 tibial arteries can be treated with cumulative length of  $\leq 15\text{cm}$
- Presence of post PTA dissection

The exclusion criteria for the TOBA-BTK study was:

- Stenosis or occlusion of inflow vessels not successfully treated
- Previous inflow vessel treatment failure

- Previous below the knee bypass
- Lesion on plantar surface of heel or Achilles tendon or exposed calcaneus

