**Table 4. TOBA-BTK Trial Baseline Clinical Assessment of Target Limb**

Parameter	Safety Sample N = 35	Performance Sample N = 32
Target Limb		
Left	40.0% (14 / 35)	34.4% (11 / 32)
Right	60.0% (21 / 35)	65.6% (21 / 32)
Number of Patent Tibial / Peroneal Vessels in the Target Limb		
1	42.9% (15 / 35)	46.9% (15 / 32)
2	42.9% (15 / 35)	37.5% (12 / 32)
3	14.3% (5 / 35)	15.6% (5 / 32)
ABI treated leg (mean ± stdev) (minimum, median, maximum)	0.95 ± 0.42 (35) (0.0, 0.94, 1.9)	0.91 ± 0.41 (32) (0.0, 0.93, 1.9)
TBI treated leg (mean ± stdev) (minimum, median, maximum)	0.49 ± 0.30 (24) (0.0, 0.47, 1.1)	0.47 ± 0.28 (23) (0.0, 0.46, 1.1)
Subject Pain Symptoms for Target Limb (check all that apply)		
No Leg Pain	48.6% (17 / 35)	46.9% (15 / 32)
Rest pain	28.6% (10 / 35)	28.1% (9 / 32)
Pain on exercise	28.6% (10 / 35)	31.3% (10 / 32)
Rutherford Clinical Category for Target Limb		
4	11.4% (4 / 35)	12.5% (4 / 32)
5	88.6% (31 / 35)	87.5% (28 / 32)

The mean pre-PTA percent diameter stenosis per lesion was 72.3%± 17.4 and 73.0%± 17.8, for the safety and performance samples, respectively. Total occlusion comprised eight of the lesions (22.2% safety sample, 24.2% performance sample). Of all dissections reported (Safety Sample), the most frequently reported worst dissection grade was B (40.5%) followed by A (35.7%), C (19.0%), and D (4.8%). The worst post-PTA dissection grades pre-Tack at Tack sites were A (21.2%), B (60.6%), and C (18.2%). The mean number of Tack implant(s) used in the Performance Sample was 2.8±2.0 with a range of 1 to 12 per lesion. Tack implant(s) were successfully delivered in 33/36 (91.7%) lesions. Three individual lesions in three subjects were not successfully treated as in each case, the catheter was not able to be advanced to the lesion location. Of the successfully placed Tack implant(s), the post-Tack implant dissection grade was 0 in 32/33 (97.0%) and B in 1/33 (3.0%). Tack implant locations to treat the dissections included anterior tibial artery (32.6%), tibio-peroneal trunk (30.4%), peroneal artery (20.7%), and posterior tibial artery (16.3%). In greater than 89.7% of the Performance Sample vessels, the Tack was placed on the proximal edge of the dissection being treated and in 76.9% of the vessels the Tack was placed on the distal edge of the dissection.

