#### 13.1.2. BASELINE ANGIOGRAPHIC REQUIREMENTS

Baseline angiographic measurements of the target lesion and target vessels (visual estimate) shall be captured to determine eligibility and include, but are not limited to the following:

- Target Lesion(s) details including Vessel location(s), Ruler location(s), Lesion length(s) (normal to normal), and pre-PTA %DS
- Lesion type(s) (De novo or restenotic)
- Reference Vessel Diameter(s) (proximal and distal)
- Inflow artery patency
- Normal artery branching and/or target vessel reconstitution
- Absence of thrombus

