#### 21.9. CENTRAL CORE LABORATORIES

To ensure that the clinical data and images are analyzed in a controlled, non-biased manner and that the results are analyzed using a standardized process, all angiograms, duplex ultrasound studies and x-rays obtained during this study will be submitted to a respective central core lab for analysis.

The core labs will be responsible for analyzing the angiograms, duplex ultrasound and x-ray images according to the study eligibility criteria, the study endpoints and requirement measurements according to this study protocol. Feedback will be provided to the sites and Sponsor regarding the quality of the tracings and images and for providing a written summary report of all angiogram, duplex ultrasound and X-ray results to the study Sponsor.

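### Entry stenosis and acute success both rest on the unblinded operator's visual estimate, and Section 19 assigns no role to the core lab's stenosis reading, although the pilot's figures do not fit the same entry threshold

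*Combined protocol and SAP*

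**What the plan says.** **Entry.** Angiographic inclusion criterion 4 (Sections 2 and 7.4.2) requires pre-PTA stenosis of at least 70%, "or is occluded (by visual estimate) and is indicated for PTA treatment with a standard balloon catheter". Section 13.1.2 confirms how this is judged: "Baseline angiographic measurements of the target lesion and target vessels (visual estimate) shall be captured to determine eligibility".

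**Acute success.** Target Lesion Success (Sections 2, 6.3 and 19.5) is <30% "residual diameter stenosis (DS), by visual estimate] without the use of a bailout stent within the target lesion upon completion of the index procedure". Procedural Success uses the same visual <30%. Criterion 8 requires <30% residual stenosis by visual estimate after PTA and before study device treatment. The study is single-arm and non-blinded.

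**Pilot.** Section 4.2 gives the TOBA-BTK entry rule as de novo lesions at least 70% "stenotic or occluded", without saying who judged it. The text after Table 4 reports: "The mean pre-PTA percent diameter stenosis per lesion was 72.3%± 17.4 and 73.0%± 17.8" (safety and performance samples). It adds: "Total occlusion comprised eight of the lesions (22.2% safety sample, 24.2% performance sample".

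**Core lab.** Under Section 9.2 all index imaging of enrolled subjects goes to the angiographic core lab. For those films Section 13.1 names only post-PTA dissections and their type. Section 21.9 is broader: images are analysed "according to the study eligibility criteria, the study endpoints and requirement measurements according to this study protocol", with a written summary to the sponsor.

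**Analysis.** Section 19.7 summarises lesion characteristics without naming a source. Section 19.9 re-analyses the primary endpoints by gender and by US versus OUS only. Stenosis severity is not among the imputation covariates listed in 19.11. The per-protocol set in 19.2 drops major eligibility violations, but the criteria for a major violation are still to be set and no data source is named.

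**The concern.** Two readings that describe the trial are made by the person using the device, who knows what is at stake: how diseased the lesion was at entry, and how good the result was at the end. For acute success the problem is sharper. The subject could be enrolled only if residual stenosis had already been called below 30%, so the stenosis component fails only if that call worsens by the end of the procedure.

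For entry severity, the pilot suggests that recorded stenosis and the stated threshold can part company. Both primary endpoints are judged against fixed external goals (12% for 30-day MALE+POD, 74% for 6-month freedom from MALE+POD), with no concurrent arm to absorb a shift in case mix. A reader of the final report will want to know how much of the enrolled disease met the 70% rule on independent measurement. The plan does not commit to showing it.

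**Working it through.** **Inputs (Section 4.2)**
- Lesions: 36 in the safety sample and 33 in the performance sample, from the statement that Tacks were delivered in 33/36 lesions.
- Mean pre-PTA stenosis (SD): 72.3% (17.4) and 73.0% (17.8).
- Total occlusions: 8 in each sample.
- Entry rule: at least 70%, or occluded.
- Assumption for steps 2 and 3: an occlusion is recorded as 100%.

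**1. Reproduce the plan's occlusion shares.** 8/36 = 22.2% and 8/33 = 24.2%. Both match, so the lesion counts are the right denominators.

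**2. Lowest mean the rule allows**, with 8 lesions at 100% and the rest at exactly 70%:
- Safety: (8×100 + 28×70)/36 = 2760/36 = 76.7%. Reported 72.3%, which is 4.4 points lower.
- Performance: (8×100 + 25×70)/33 = 2550/33 = 77.3%. Reported 73.0%, which is 4.3 points lower.

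The raw means exceed 70%, so a plain comparison with the threshold shows nothing. The conflict appears only once the occlusions are counted.

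**3. Implied mean of the non-occluded lesions**, (n×mean − 800)/(n − 8):
- Safety: (36×72.3 − 800)/28 = 64.4%.
- Performance: (33×73.0 − 800)/25 = 64.4%.

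Rounding of the reported means moves these only within 64.3% to 64.5%.

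**4. Check without fixing the occlusions at 100%.** If every lesion lay between 70% and 100%, the largest possible sample SD at mean m is √[(100 − m)(m − 70)·n/(n − 1)]:
- Safety: √(27.7 × 2.3 × 36/35) = 8.1, against 17.4 reported.
- Performance: √(27.0 × 3.0 × 33/32) = 9.1, against 17.8 reported.

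The reported SDs are about twice the maximum, so some recorded pilot values were below 70%.

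**5. Trace the core-lab reading through Section 19.** No analysis of the primary endpoints (19.8.1, 19.8.2, 19.9 to 19.11) and neither acute-success definition (19.5) names core-lab diameter stenosis. Two places could use it without saying so: the lesion characteristics in 19.7 and the per-protocol exclusions in 19.2.

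**The case against.** The strongest reply is that the protocol defines severity by visual estimate, so subjects chosen that way are the stated population, and a lower reading by another method is a difference between readers. The pilot was a small, de novo-only feasibility study whose reader is not identified, so it does not show that this trial will enrol sub-threshold lesions. Clinical severity is controlled separately by Rutherford class 4 or 5 and by WIfI wound and infection grades, and 88.6% of the pilot safety sample was Rutherford 5. The acute-success endpoints are observational, carry no hypothesis, openly state their method, and play no part in study success (19.12). All of this stands, and it keeps the point away from the primary tests.

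A reader might go further and infer that the enrolled disease is milder than that behind the performance goals, so the comparison leans towards the device. The documents do not support that. They give no stenosis figures for the populations behind the 74% and 12% goals. They do not show that percent stenosis among non-occluded lesions predicts MALE or death, and Section 4.1 itself notes a discrepancy between patency and clinical outcomes.

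A reader might also infer that the core lab's reading is used nowhere. That is too strong: Section 21.9 has it read films against the eligibility criteria and report to the sponsor, and 19.7 leaves its source open. What can be said is that its use is unspecified.

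The objection does not answer the acute-success issue. Being descriptive does not make a result less open to the operator's optimism, and an independent reading appears to be within reach.

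**Conclusion.** The point holds as an inexpensive improvement to the analysis plan. The pilot means sit 4.4 and 4.3 points below the floor that the 70%-or-occluded rule implies, and non-occluded lesions averaged about 64%. These figures assume occlusions were recorded as 100%. The SD check does not need that assumption, and it shows that at least some recorded values were below threshold. The cause may be a reader difference or enrolment below threshold, and the documents cannot separate the two. Nor do a mean and an SD fix what share of lesions fell below 70%, so no share is claimed.

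For this trial, the gap is that Section 19 leaves core-lab stenosis out of every named analysis of the primary endpoints and of acute success, and scores acute success on an operator estimate that had to be favourable for the subject to be enrolled. A bias in the primary comparisons is possible but not shown. The primary tests, goals and sample size are unaffected.

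**What to change.** 1. **Section 19.5** (with 2, 6.3 and 24 to match): score Target Lesion Success and Procedural Success on core-lab residual diameter stenosis at the end of the index procedure, with the operator's estimate shown beside it.
2. **Section 19.7:** report baseline diameter stenosis from the core lab beside the site estimate, with the share of target lesions below 70% by core lab.
3. **Section 19.9:** add a descriptive re-analysis of both primary endpoints (point estimate and 95% confidence interval, no test) in subjects with at least one target lesion that is at least 70% stenosed or occluded by core-lab reading.

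Eligibility stays visual, and the primary tests, performance goals and sample size do not change.

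**Cost.** Mainly plan wording, since the core lab already receives every index angiogram. One condition must be checked: Section 13.1 names only dissections for the index films, so the core-lab protocol must be confirmed to include pre-PTA and final diameter stenosis. If it does not, those readings have to be added. Acute success may also look slightly less favourable than on the operator's estimate.
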